14.6 Expedited Reporting

Table 14.6 indicates what events must be reported expeditiously.

Table 14.6 Criteria for Expedited Reporting

Time point	What to report
From signing of the consent to study completion	• All UPs
For the time period beginning at treatment through 90 days following cessation of treatment, or 30 days following cessation of treatment if the subject initiates new anticancer therapy, whichever is earlier	 All SAEs regardless of relationship to protocol therapy All UPs and AEs that meet the definition of a UP AESIs* Secondary malignancy Pregnancies and lactation
From Day 1 of protocol therapy up to 90 days post-last polatuzumab vedotin dose	Pregnancies and lactation
Post Safety Follow-Up to removal from study	 All SAEs that are considered possibly, probably or definitely related to protocol therapy.

^{*} AESIs (except secondary malignancy) do not require an expedited report unless the event results in unplanned hospitalization or prolongation of hospitalization. However, they must still be reported through the routine mechanism in the eCRFs, and to Genentech within the timelines indicated in Section 14.8.

NOTE: All events reported expeditiously require follow-up reporting until the event is resolved, stabilized, or determined to be irreversible by the investigator.

The DCC should be consulted prior to ending the follow-up of events that have stabilized.

14.6.1 Expedited reporting guidelines (COH only)

14.6.1.1 To the COH DSMC/IRB

Serious Adverse Events that require expedited reporting and unanticipated problems will be reported according to the approved City of Hope Clinical Research Adverse Event and Unanticipated Problem policy. This includes all SAEs and UPs that meet COH DSMC/IRB expedited reporting criteria that occurred at COH and non-COH sites. For non-COH sites, the DCC will be responsible for reporting (see Section 14.6.2).

14.6.1.2 To Participating Investigators

Report all expedited reportable AEs to participating investigators as an IND Safety Report occurring within 30 calendar days of receipt of sponsor (lead site) notification, and indicate whether or not a protocol and/or consent form change is required. A cover letter will indicate the protocol title, the IND#, whether the FDA was informed (if applicable), and, for non-COH sites, a statement that the report should be submitted to their local IRB for review if applicable per local IRB policy.

• Forward to participating sites all IND safety reports received from Genentech, indicating whether a consent form or protocol change is required within 30 days of notification to Study PI.

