5.2 Salvage and Consolidation: Treatment Cycle Definition

In the absence of a delay due to toxicity, each treatment cycle lasts 21 days with a \pm 3 day window during both Salvage and Consolidation.

- Salvage PolaR-ICE (Section 5.6):
 - Day 1 of each cycle will be defined as the first day of administration of Pola.
 - If Pola is not administered, then Day 1 will be defined as the day of administration of rituximab.
- Consolidation Pola (Section 5.7):
 - Day 1 of each treatment cycle is defined by the day of administration of Pola.

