6.0 ANTICIPATED ADVERSE EVENTS

6.1 Polatuzumab vedotin

The Investigator's Brochure (IB) is the primary source for safety information. Refer to the most recent IB, which is updated periodically, for current information on polatuzumab vedotin.

The most common adverse reactions (≥20%) include neutropenia, thrombocytopenia, anemia, peripheral neuropathy, fatigue, diarrhea, pyrexia, decreased appetite, and pneumonia.

Table 6.1 (polatuzumab vedotin IB V11, October 2019) lists all expected serious adverse drug reactions (SADRs) for polatuzumab vedotin. These SADRs were selected based on individual and aggregate assessment, medical review, and prior reports of the adverse reactions in clinical trials. Frequencies are based on pooled clinical trial data and/or single clinical trial data using only related serious adverse events as noted.

Table 6.1 Serious adverse drug reactions (SADRs) to polatuzumab vedotin in B-cell lymphomas including indolent non-Hodgkin lymphoma and diffuse large B-cell lymphoma considered expected for safety reporting purposes

	SADRs	(Cumulative clinical trial exposure (N=635)		
System Organ Class		All SADRs N* (%)	Fatal SADRs N* (%)	Life-threatening SADRs N* (%)
Blood and lymphatic disorders	Leukopenia	2 (0.3)	n/a	n/a
	Febrile neutropenia	43 (6.7)	n/a	n/a
	Neutropenia	11 (1.7)	n/a	n/a
Nervous system disorders	Peripheral motor neuropathy	3 (0.5)	n/a	n/a
	Peripheral sensory neuropathy	3 (0.5)	n/a	n/a
Infections and infestations	Pneumonia	10 (1.57)	n/a	n/a
Gastro-intestinal disorders	Abdominal pain	2 (0.3)	n/a	n/a
	Diarrhea	9 (1.4)	n/a	n/a
	Vomiting	2 (0.3)	n/a	n/a
General disorders and administration	Pyrexia	8 (1.3)	n/a	n/a

n/a = fatal or life-threatening SADRs are not considered expected.

All fatal or life-threatening SADRs are considered unexpected for regulatory purposes.

Table 6.2 summarizes commonly reported reactions in study GO29365 (NCT02257567) where Pola was combined with chemotherapy.

Table 6.2 Adverse reactions occurring in >10% of patients with relapsed or refractory DLBCL and ≥5% more in the polatuzumab vedotin (Pola) plus bendamustine and rituximab (BR) product group.

Adverse Reactions by Body System	Pola + BR (n=45) All Grades (%)	BR (n=39) All Grades (%)
Blood and Lymphatic System Disorders		
Neutropenia	49	44
Thrombocytopenia	49	33
Anemia	47	28
Lymphopenia	13	8
Nervous System Disorders		
Peripheral neuropathy	40	8
Dizziness	13	8
Gastrointestinal Disorders		
Diarrhea	38	28
Vomiting	18	13
General Disorders		

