14.7 Reporting to the FDA

The study PI (or designee) will be responsible for contacting the Office of IND Development and Regulatory Affairs (OIDRA) at COH to ensure prompt reporting of safety reports to the FDA. OIDRA will assist the PI with the preparation of the report and submit the report to the FDA in accordance with the approved City of Hope Clinical Research Adverse Event and Unanticipated Problem policy.

Serious Adverse Events meeting the requirements for expedited reporting to the Food and Drug Administration (FDA), as defined in 21 CFR 312.32, regardless of the site of occurrence, will be reported as an IND safety report using the MedWatch Form FDA 3500A for Mandatory Reporting.

The criteria that require reporting using the MedWatch 3500A are:

- Any unexpected fatal or life threatening adverse experience associated with use of the drug must be reported to the FDA no later than 7 calendar days after initial receipt of the information [21 CFR 312.32(c)(2)]
- Any adverse experience associated with use of the drug that is both serious and unexpected must be submitted no later than 15 calendar days after initial receipt of the information [21 CFR 312.32(c)(1)]
- Any follow-up information to a study report shall be reported as soon as the relevant information becomes available. [21 CFR 312.32(d)(3)]

The final IND report will be distributed to the Study PI and DCC. If it is determined that the IND safety report requires a change to the protocol or the consent form, the DCC will include instructions to participating sites for local IRB reporting.

In addition, on behalf of the study PI, OIDRA will submit annually within 60 days of the anniversary of the date the IND went into effect, an annual report to the FDA which is to include a narrative summary and analysis of the information of all FDA reports within the reporting interval, a summary report of adverse drug experiences, and history of actions taken since the last report because of adverse drug experiences.

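### For events that go to the FDA in 7 or 15 days, Section 14.6.1.2 lets participating investigators be told up to 30 days after the lead site, longer than one 21-day cycle, and nothing else assures earlier notice

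*Combined protocol and SAP*

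**What the plan says.** **Notice to sites.** Section 14.6.1.2 instructs the lead site: "Report all expedited reportable AEs to participating investigators as an IND Safety Report occurring within 30 calendar days". The clock runs from the lead site's own notification ("within 30 calendar days of receipt of sponsor (lead site) notification"). The accompanying letter states whether a protocol or consent change is needed and, if applicable, whether the FDA was informed. IND safety reports received from the industry partner are also forwarded to sites, "indicating whether a consent form or protocol change is required within 30 days of notification to Study PI".

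**Notice to the FDA.** Under Section 14.7, an unexpected fatal or life-threatening event associated with the drug "must be reported to the FDA no later than 7 calendar days after initial receipt of the information". One that is serious and unexpected "must be submitted no later than 15 calendar days after initial receipt of the information". Section 6.1 adds, for polatuzumab vedotin: "All fatal or life-threatening SADRs are considered unexpected for regulatory purposes". On distribution, Section 14.7 says: "The final IND report will be distributed to the Study PI and DCC". It mentions participating sites only for local IRB instructions when a protocol or consent change is required, and gives no time limit for these.

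**Other clocks.** Non-COH sites report to the coordinating center (DCC) and Study PI within 24 hours (Section 14.6.2.1). The industry partner receives expedited SAE reports within 15 days (Table 14.8).

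**Dosing.** Section 5.2 states that, without a toxicity delay, "each treatment cycle lasts 21 days", with a window of 3 days either way.

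**The concern.** Information reaches the lead site within a day and must leave for the FDA within 7 or 15 days, but it may take 30 days to reach the investigators at the other sites. Those investigators give the next dose, judge the expectedness and attribution of their own patients' events (Section 14.1) and explain the risks at consent (Section 17.4). All three tasks depend on knowing of a similar serious event elsewhere. For polatuzumab vedotin, Section 6.1 puts every fatal or life-threatening reaction in the unexpected class, so the gravest drug-related events fall on the 7-day FDA clock and have the longest possible lag to sites.

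At stake is whether a site that follows the plan exactly could give another cycle without knowing of a fatal event that the sponsor has already reported.

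**Working it through.** The 30 days is a rule and not a derived figure, so there is nothing to reproduce. The check compares the clocks and then asks what fits into the gap.

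**Inputs.** Site limit 30 days (14.6.1.2). FDA limits 7 and 15 days (14.7). Cycle 21 days, range 18 to 24 (5.2). Accrual of 40 evaluable patients, maximum 53, in 24 months (12.3). Assumptions: both clocks start on the same day, accrual is even, and a month has 30.44 days.

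**1. Lag of the site limit behind the FDA limit**
- Unexpected fatal or life-threatening: 30 − 7 = 23 days.
- Other serious and unexpected: 30 − 15 = 15 days.

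**2. Day 1 doses before a site is told, for a patient on continuous cycles**

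Mean = window / cycle length.

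| Window | 18-day cycle | 21-day cycle | 24-day cycle | Doses possible |
|---|---|---|---|---|
| 30 days | 1.67 | 1.43 | 1.25 | 1 to 2 |
| 15 days | 0.83 | 0.71 | 0.62 | 0 or 1 |
| 7 days | 0.39 | 0.33 | 0.29 | 0 or 1 |

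Over the full 30 days at least one further dose falls due whatever the cycle length. For the lag alone, 23 / 21 = 1.10, so one dose falls due on a 21-day cycle but is not certain on a 24-day cycle (23 / 24 = 0.96). In the 15-day lag one further dose is likely but not assured (15 / 21 = 0.71).

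**3. Enrolment during the lag**

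Rate = 40 / 24 / 30.44 = 0.0548 patients per day, study-wide.
- 23 days: 0.0548 × 23 = 1.3 patients.
- 15 days: 0.0548 × 15 = 0.8 patients.

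At 53 patients the rate is 0.0726 per day, giving 1.7 and 1.1. If the five sites accrue equally (an assumption), four fifths of these are at the other four sites: 1.0 and 0.7 at the 40-patient rate.

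**4. Does another section assure earlier notice?**
- *Safety lead-in (11.2, 12.1.1).* One treatment-related death in the first two cycles is one unacceptable toxicity. Accrual may then continue to six patients.
- *Non-relapse mortality after ASCT (12.4).* The rule needs a second death within 100 days.
- *Consolidation (12.5).* The rule starts at six treated patients and needs a rate of 33% at a six-monthly review. One patient in six is 17%.
- *Protocol Management Team (16.3).* Site investigators are members and SAEs are discussed, but meetings are only recommended and no interval is given.
- *Central registration (4.2).* The DCC can hold new registrations. Nothing requires it to tell a site about an event when it registers a patient, and doses for patients already enrolled do not pass through it.

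A single death therefore need not trigger any of these rules, and none of these sections sets a date by which sites must hear of it.

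**The case against.** The strongest reply is that there is no conflict. The two sections set maximum times for different recipients, a lead site can comply with both, and faster notice is always allowed. That stands. A reader might infer a contradiction or a regulatory breach, but the documents support neither: they nowhere say that the site clock must equal the FDA clock, and the text of the regulation and the sponsor's adverse event policy is not included.

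Three points on scope also stand.
- The reports are not always the same report. Table 14.6 makes all SAEs expedited regardless of relationship, and the Section 14.6.1.2 letter says whether the FDA was informed only if applicable. Many events on the 30-day clock may have no FDA deadline.
- Enrolment is not blind. The DCC verifies slots, registers every participant and learns of non-COH events within 24 hours, and lead-in accrual is restricted after one unacceptable toxicity.
- Earlier notice would not in itself update a consent form. Revisions need IRB approval first (17.3), and site consent amendments need DCC review (17.4).

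The reply does not show where a site would learn of the event sooner. The existing controls act mainly on accrual and dose level. None assures that an investigator about to give the next cycle has been told.

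**Conclusion.** The concern holds for events that meet the Section 14.7 criteria. For these, participating investigators may be told up to 23 or 15 days after the FDA deadline, and the 30-day limit is longer than one cycle. This is a weakness in a permitted maximum and not an error in the plan.

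The result assumes that the lead site uses the full 30 days, that both clocks start together, and that the patient is on uninterrupted cycles.

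Three larger readings are tempting but unsupported.
- *Every treated patient elsewhere gets another dose.* Salvage is two or three cycles, and consolidation starts between Day +30 and Day +60 after transplant (Day +75 if delayed). Patients at a last dose or in the transplant interval receive no polatuzumab vedotin in the window.
- *About 1.7 patients enrol unaware at the 40-patient rate.* That is a full month's accrual (40 / 24) at all sites, including the lead site. The lag itself holds about 1.3 or 0.8, registered by a center that knows of the event.
- *Sites are the last to be told.* The timing for the DSMC and IRB is in a policy outside the documents, so the order cannot be established.

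**What to change.** In Section 14.6.1.2, for events reported to the FDA under Section 14.7, require the IND safety report to reach participating investigators no later than the Section 14.7 deadline for that event: 7 calendar days for unexpected fatal or life-threatening events and 15 for other serious and unexpected ones. Leave other expedited events at 30 days. Let the statement on a protocol or consent change follow within 30 days.

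For IND safety reports from the industry partner, ask that the report be forwarded promptly on receipt, and keep the 30 days for the protocol or consent determination. The present sentence can be read as attaching the 30 days to either step. The documents give no source for a specific figure such as 15 days here.

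On a 21-day cycle, the mean number of Day 1 doses before notice would fall from 1.43 to 0.33 (7-day events) or 0.71 (15-day events). Study-wide enrolment before notice, at 40 patients over 24 months, would fall from 1.6 (0.0548 × 30) to 0.4 or 0.8.

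The cost is protocol wording and an email of a report already written for the FDA. The downside is a possible second message to sites. No dose, stopping rule or sample size changes.

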14.6.2 Expedited reporting guidelines (non-COH sites only)

14.6.2.1 To the DCC/Study PI

All events that meet the criteria specified in Table 14.6 will be reported to the DCC and Study PI within 24 hours of notification that the event met the expedited reporting criteria.

- 1. Sites are to report to their local IRB per their site's specific institutional and IRB guidelines. As soon as possible, non-COH sites will provide to the COH DCC copies of the IRB submission and corresponding IRB response.
- 2. Document/describe the AE/UP on each of the following:
 - a. MedWatch 3500A or local IRB submission document*
 MedWatch 3500A is downloadable form at http://www.fda.gov/medwatch/getforms.htm
 *The local IRB submission document may be used if the document template is approved by the DCC
 - b. Expedited Reporting Coversheet. A modifiable Microsoft Word document is available from the DCC. An electronic signature on the document will be accepted.
- 3. Scan and email above documents to the Study PI ([contact]) and [contact] with the subject title as "[PolaR-ICE as initial salvage for R/R DLBCL] SAE COH IRB #20148".
 - a. If available, sites may include the local IRB submission for this event in the submission.
- 4. If an email receipt from DCC personnel is not received within one working day, please email [contact].

14.7 Reporting to the FDA

The study PI (or designee) will be responsible for contacting the Office of IND Development and Regulatory Affairs (OIDRA) at COH to ensure prompt reporting of safety reports to the FDA. OIDRA will assist the PI with the preparation of the report and submit the report to the FDA in accordance with the approved City of Hope Clinical Research Adverse Event and Unanticipated Problem policy.

Serious Adverse Events meeting the requirements for expedited reporting to the Food and Drug Administration (FDA), as defined in 21 CFR 312.32, regardless of the site of occurrence, will be reported as an IND safety report using the MedWatch Form FDA 3500A for Mandatory Reporting.

The criteria that require reporting using the MedWatch 3500A are:

- Any unexpected fatal or life threatening adverse experience associated with use of the drug must be reported to the FDA no later than 7 calendar days after initial receipt of the information [21 CFR 312.32(c)(2)]
- Any adverse experience associated with use of the drug that is both serious and unexpected must be submitted no later than 15 calendar days after initial receipt of the information [21 CFR 312.32(c)(1)]
- Any follow-up information to a study report shall be reported as soon as the relevant information becomes available. [21 CFR 312.32(d)(3)]

The final IND report will be distributed to the Study PI and DCC. If it is determined that the IND safety report requires a change to the protocol or the consent form, the DCC will include instructions to participating sites for local IRB reporting.

In addition, on behalf of the study PI, OIDRA will submit annually within 60 days of the anniversary of the date the IND went into effect, an annual report to the FDA which is to include a narrative summary and analysis of the information of all FDA reports within the reporting interval, a summary report of adverse drug experiences, and history of actions taken since the last report because of adverse drug experiences.

14.8 Reporting to Industry Partner

The Study PI (or designee) will:

Report to Genentech per the guidelines provided in Table 14.8.
 Email: [contact]; [contact]

Table 14.8 Timeframes for Reporting to Genentech

Type of Report	Reporting Timeframes to Genentech
Pregnancy	Within 30 calendar days of being aware of the event using the Genentech Pregnancy Reporting Form.
All expedited SAE reports Post-study SAE reports	Within 15 calendar days of being aware of the event via a MedWatch 3500A form.
AESIs	Within 15 calendar days of the awareness event.
Aggregate safety reports	Forward to Genentech every 6 months (e.g. at time of COH PMT report).
Special Situation Reports*	Within 30 calendar days of the awareness event.
Product complaints**	Within 15 calendar days of the awareness event.
	Product complaints without an AE should be reported by calling:
	PC [contact] (M-F : 5am to 5pm PST)

- Assist Genentech in investigating any SAE and will provide any follow-up information reasonably requested by Genentech.
- *Special Situations Reports: In addition to all SAEs, pregnancy reports and AESIs, the following Special Situations Reports should be collected even in the absence of an Adverse Event and transmitted to Genentech:
 - Data related to polatuzumab vedotin usage during breastfeeding
 - Data related to overdose, abuse, misuse, or medication error (including potentially exposed or intercepted medication errors)
 - In addition, reasonable attempts should be made to obtain and submit the age or age group of the patient, in order to be able to identify potential safety signals specific to a particular population
- **Product Complaints: A Product Complaint is defined as any written or oral information received from a complainant that alleges deficiencies related to identity, quality, safety, strength, purity, reliability, durability, effectiveness, or performance of a product after it has been released and distributed to the commercial market or clinical trial.

- Fax to Genentech/Roche Safety copies of all written IND safety reports submitted to the FDA:
 - [contact] or [contact]
- Email to Genentech Drug Safety CTV all IND annual reports and the final study report submitted to the FDA:

Email: [name] [contact]

14.9 Case Transmission Verification of Single Case Reports

The Sponsor agrees to conduct the Case Transmission verification to ensure that all single case reports have been adequately received by Genentech via the investigator emailing Genentech a Quarterly linelisting documenting single case reports sent by the investigator to Genentech in the preceding time period.

The periodic line-listing will be exchanged within seven (7) calendar days of the end of the agreed time period. Confirmation of receipt should be received within the time period mutually agreed upon.

If discrepancies are identified, the Sponsor and Genentech will cooperate in resolving the discrepancies. The responsible individuals for each party shall handle the matter on a case-by-case basis until satisfactory resolution. The sponsor shall receive reconciliation guidance documents within the 'Activation Package'.

Following Case Transmission Verification, single case reports which have not been received by Genentech shall be forwarded by the investigator to Genentech within five (5) calendar days from request by Genentech.

At the end of the study, a final cumulative Case Transmission Verification report will be sent to Genentech

14.10 Queries

Queries related to the Study will be answered by the investigator. However, responses to all safety queries from regulatory authorities or for publications will be discussed and coordinated between the Parties. The Parties agree that Genentech shall have the final say and control over safety queries relating to polatuzumab vedotin. The investigator agrees that it shall not answer such queries from regulatory authorities and other sources relating to polatuzumab vedotin independently but shall redirect such queries to Genentech.

Both Parties will use all reasonable effort to ensure that deadlines for responses to urgent requests for information or review of data are met. The Parties will clearly indicate on the request the reason for urgency and the date by which a response is required.

